9.6 Critical Event Identification and Reporting

In addition, we will report critical events (CEs) to DAIDS and other entities to which we are responsible, including IRBs. Critical events include the following classes of events: unanticipated problems involving risks to participants or others, serious noncompliance, continuing noncompliance, suspension or termination of EC/IRB approval, and suspected research misconduct. The time period for reporting CEs to DAIDS is from the date of study start up to the publication of all related manuscripts resulting from the study.

10 Study Administration, Data Handling and Record Keeping

10.1 Confidentiality

Information about study participants will be kept confidential and managed according to the principles of the Health Insurance Portability and Accountability Act of 1996 (HIPAA).

10.2 Data Collection and Management

All clinical and laboratory information required by this protocol is to be present in the source documents. All protocol-required visits are to be recorded on the CRFs and keyed into the database unless otherwise specified.

We will use Clinical Research IO, CPIO, as the study clinical data management system. The site data managers and clerks will be responsible for manually entering quantitative data, not already being collected routinely and required for the evaluation, into a study database. Site databases and the merged analytical datasets will be stored on password-protected, encrypted servers. Scheduled backups will be performed on a daily, weekly, and monthly basis. Personal identifiers will be suppressed from the analytic dataset prior to the data analysis phase of the study. Any paper registers, forms, or records that are reviewed in order to abstract data or cross-check missing data will not be removed from the secure, programmatic area where they are stored.

Data will be validated on entry, using range and consistency checks. Quality control procedures will include review of CRFs for completion and correctness. Logical data checks will also be performed on the data. Incomplete and incorrect data queries will be sent back to sites electronically for error resolution. Errors will be reviewed and corrected on a weekly basis. The study will be monitored by internal data monitors.

10.3 Records Retention

Study records (source documents, signed informed consent forms, IRB correspondence and approval letters, and screening logs) will be kept in a secure location accessible only to authorized study staff, investigators, and monitors. All records will be archived in a secure storage facility for at least ten years after the completion of the study.

11 Study Monitoring, Auditing, and Inspecting

11.1 Study Monitoring Plan

This study will be conducted under ICH E6 with good clinical practice compliance. Audits of the Emory site and study will be performed by the DAIDS-appointed study-monitoring team as described in [Section 9.5.1](#). The Investigator will permit study-related monitoring, audits, and inspections by the EC/IRB, the sponsor, site monitors, Office of Human Research Protections (OHRP), and other local, US, or international regulatory entities (e.g, FDA, EMA, and other regulatory agencies), and University compliance and quality assurance groups of all study related documents (e.g. source documents, regulatory documents, data collection instruments, study data etc.). The Investigator will ensure the capability for inspections of applicable study-related facilities (e.g. pharmacy, diagnostic laboratory, etc.).

Participation as an investigator in this study implies acceptance of potential inspection by local, US, or international regulatory entities (e.g, EMA) and applicable University compliance and quality assurance offices.

Monitoring visits may be conducted on-site or remotely. Remote visits may include remote source document verification using methods specified for this purpose by NIAID. Remote monitoring visits may be performed in place of, or in addition to onsite visits to ensure the safety of study participants and data integrity (51). The site will make available study documents for site monitors to review utilizing a secure platform that is HIPAA and 21 CFR Part 11 compliant. Potential platform options include: Veeva SiteVault, site-controlled SharePoint or cloud-based portal, direct access to Electronic Medical Record (EMR), and Medidata Rave Imaging Solution. Other secure platforms that are 21 CFR Part 11 compliant may be utilized, as allowed by the DAIDS Office of Clinical Site Oversight (OCSO).

12 Ethical Considerations

This study is to be conducted in accordance with applicable US government regulations and international standards of Good Clinical Practice, and applicable institutional research policies and procedures.

This protocol and any amendments will be submitted to a properly constituted independent Ethics Committee (EC) or Institutional Review Board (IRB), in agreement with local legal prescriptions, for formal approval of the study conduct. The decision of the EC/IRB concerning

the conduct of the study will be made in writing to the Investigator before commencement of this study.

12.1 Risks

The rationale for the dosing schedule is as follows: 14 days of imatinib exposure is required to observe an effect on myelopoiesis (the primary end-point), and 28 days will provide additional information on safety. We do not expect that imatinib will cause significant AEs in healthy normal volunteers when given for this duration. While asymptomatic elevations in aminotransferase levels are often seen in patients within 2-8 weeks after starting imatinib, marked increases in ALT are usually only observed after 6 months of imatinib therapy.

Importantly, the toxicity of imatinib is dose-related. We will minimize risk by starting with a very low dose (50 mg/day) and escalate carefully only after safety data on the lower dose has been reviewed for acceptability. The DSMB must recommend proceeding to the next dose level before it will be initiated. Volunteers will be very closely monitored for adverse events at a US cancer center setting highly experienced with imatinib therapy. Visits with a safety evaluation are at study days 1, 3, 7, 14, 15, 21, 28 and 42.

Imatinib is well tolerated in CML patients, and a maximal tolerated dose has not been defined, but >800mg/day is rarely used. Most adverse effects, even at the highest doses, are grade 1 (mild) or grade 2 (moderate). Most patients have a reduction in the Hgb level of 1 to 2 mg/dL; the hemoglobin level typically increased to base-line values or higher with continued therapy. Drug induced anemia during long-term administration has been rarely seen. Neutropenia occurs in chronic phase CML patients treated with imatinib at the onset of blast crisis, but is unlikely to occur in patients receiving low doses in the absence of hematological disease. Inhibition of normal hematopoiesis does not occur in Philadelphia chromosome negative patients, although further clinical assessment will be required to ensure this. In summary, we expect these doses of imatinib to be very safe.

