2.1 Primary Objective

- To determine the effects of different doses of imatinib on myelopoiesis in adults when given alone
- Primary Safety Objective: To determine the safety of different doses of imatinib in adults

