3.2 Study Endpoints

3.2.1 Primary Study Endpoints

- The primary endpoint is the change in the number of myelomonocytic cells in the blood between baseline and day 14 of imatinib (imatinib alone).
- The primary safety endpoint will be grade 3 or 4 events and SAEs. All AEs regardless of grade will be recorded and monitored. Safety will be primarily determined by the percent of participants on study who experience a grade 3 or 4 AE or a serious adverse event (SAE) that are considered related to the study drug. An SAE is defined as any untoward medical occurrence that meets any of the following criteria:
 - Results in death, or is life-threatening
 - Results in participant hospitalization or prolongation of existing hospitalization
 - Results in persistent or significant disability/incapacity
 - Is a congenital anomaly/birth defect

Other medically important conditions will also be assessed. These conditions include important medical events that may not be immediately life-threatening or result in death or hospitalization but may jeopardize the participant or may require intervention to prevent one of the outcomes listed in the definition above.

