8.1 Sample Size Justification and Statistical Analysis

The primary objectives are to determine the effect of imatinib on the numbers of myelomonocytic cells in the blood, assessed as the change between baseline and day 14 of

imatinib only administration. Secondary objectives include analysis of PK measurements, bacterial killing, proteomic evaluations, and immune function evaluations. We will enroll a total of 48 evaluable participants total, 12 across 4 doses of imatinib (50, 100, 200 and 400mg). 12 participants were already enrolled at the 50 mg dose, and 4 at the 100mg dose in the previous version of the protocol.

With 12 participants per dosage arm (N=48), we will have 80% power to reject the null hypothesis of no change versus the alternative hypothesis that imatinib induces an increase in the absolute numbers of myelomonocytic cells per uL of blood that is at least 0.41 of the standard deviation (SD) of the change for the cohort overall and 90% power to detect a 0.48 SD. Our primary analysis will use a linear mixed model that pools data from all time points, thus we anticipate having more power by leveraging the within-person correlation between individuals.

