There is a chance that participants will not be enrolled on all doses. Given what is known about the safety profile of imatinib, we anticipate that at least one dose will be fully enrolled. By the same rationale above, we will have 80% (90%) power to detect an increase of at least 0.89 (1.03) of a SD of the mean number of myelomonocytic cells in a specific dosage strata (using 12 per stratum). We will also have sufficient power to detect differences in effects induced by different doses. For example, comparing dose groups with a two-sample t-test, with 12 participants per dosage stratum, we would have 80% power to detect a 2.3×10^3 cells/uL difference between two arms in the change from baseline in the myelomonocytic cell count assuming a SD similar to that seen in a recent macaque study. In a preclinical study of imatinib in *Mtb*-infected antibiotic-treated treated macaques, the mean number of myelomonocytic cells increased from 1.47 ± 0.96 in controls to 3.78 ± 1.89 in imatinib treated animals, with a mean difference of 2.31 (all values indicate thousands of cells/uL). Thus we are adequately powered to detect dose-specific differences on the order of what was seen in the macaques. Further, in a supportive analysis, we will also pool the arms in order to borrow strength across the doses to fit a dose-response curve.

Myelopoiesis will be determined by estimating the absolute number of myelomonocytic cells per uL of blood using the WBC and a manual differential, as noted above. We hypothesize that, on

average, increases in myelopoiesis will occur (and the 95% CI for the change in myelopoiesis over time will exclude 0).

The same mixed model can be used for the analyses of all primary and secondary endpoints where data from all arms and time points are put into one model for the myelopoiesis count outcome. This approach should generally be a more powerful approach than the paired t-test for the change from baseline, as it is leveraging the within person correlation at all time points.

Notation: Note that day 28 terms, not shown here, can also be included similarly for those with 28-day imatinib only dosing.

Let Y_{ij} represent the cell count for individual i at time j , where $j=\text{day } 0, 14$.

Thus, Y_{i0} = count at baseline, Y_{i14} = count at day 14 for individual i .

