Similarly, let $t_{14_{ij}}$ = day14 indicator and $dose_{k_{ij}}$ = dose k indicator for individual i , time j , where $k=2,3,4$. Let r_i be the random intercept term for person i and let error_{ij} be the mean 0 independent error term for person i at time j .

$$Y_{ij} = b_0 + b_1 t_{14_{ij}} + b_2 t_{14_{ij}} * dose_{2_{ij}} + b_3 t_{14_{ij}} * dose_{3_{ij}} + b_4 t_{14_{ij}} * dose_{4_{ij}} + r_i + \text{error}_{ij}$$

b_0 = baseline myelopoiesis

b_1 = day14 change from baseline for dose 1

b_2 = difference between dose 2 and dose1 day14 change from baseline

b_3 = difference between dose 3 and dose1 day14 change from baseline

b_4 = difference between dose 4 and dose1 day14 change from baseline

$(4b_1+b_2+b_3+b_4)/4$ is the average Day 14 change from baseline pooled across the 4 doses in, i.e. the primary endpoint

$b_2 - b_3$ is the between dose difference in the day14 change from baseline for dose 2 and 3; similar comparisons can be for each distinct pair of doses for day14 change from baseline.

AE analysis

We will estimate proportion of clinical and laboratory adverse events, along with 95% exact Clopper-Pearson CI. AE rates will be summarized separately by dose and then overall. All participants who take at least 1 dose will be included in assessments of safety.

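### The Version 5.0 adverse event analysis makes no comparison across doses and counts events over a window that mixes dose with regimen; days 1-14 rates and a supportive exact trend test would help.

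*Combined protocol and SAP*

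**What the plan says.** All references are to Version 5.0.

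- Section 2.1: "Primary Safety Objective: To determine the safety of different doses of imatinib in adults".
- Section 3.2.1: "Safety will be primarily determined by the percent of participants on study who experience a grade 3 or 4 AE", or a serious AE (SAE), judged related to study drug.
- Section 12.1: "Importantly, the toxicity of imatinib is dose-related". Starting low and escalating stepwise rests on this.
- Section 8.1, AE analysis: "We will estimate proportion of clinical and laboratory adverse events, along with 95% exact Clopper-Pearson CI". Then: "AE rates will be summarized separately by dose and then overall".
- Section 8.1, sample size: "We will enroll a total of 48 evaluable participants total, 12 across 4 doses of imatinib (50, 100, 200 and 400mg"). Twelve at 50 mg and four at 100 mg came from the previous protocol version.
- Section 8.1, for the myelomonocytic cell count only: "we will also pool the arms in order to borrow strength across the doses to fit a dose-response curve".
- Study Summary, Safety: AE incidence is taken over all follow-up time.
- Section 1.4: the first 16 volunteers were under a version that gave imatinib together with rifabutin and isoniazid between days 14 and 28. Toxicity at 100 mg in combination was unacceptably high.
- Sections 8.1.1.2 and 8.1.1.3: a regression-spline (MARS) search for drug concentrations associated with AEs. A note heads each section. It says the text was kept because such associations may be looked at in the earlier participants at 50 and 100 mg.

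**The concern.** The plan relies on dose order to justify escalation and uses it for the cell count, but not in analysing AEs. Each dose is described on its own and then all are averaged, so the results contain no direct statement on whether harm rises with dose. The overall rate averages an 8-fold dose range and is the true rate of no particular dose.

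The second problem is the window. Over all follow-up, the two lowest doses carry combination-therapy time and the two highest carry none. Since Section 1.4 reports toxicity under the combination, events in that period could flatten or reverse an imatinib dose gradient, and could be read as low-dose imatinib harm. At stake is how clearly the trial informs the choice of doses for later studies.

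**Working it through.** **Inputs.** 12 per dose, four doses, N = 48; two-sided 95% Clopper-Pearson intervals (Section 8.1). The documents give no expected AE rate by dose, and Section 3.1.2 expects no grade 3 or 4 events. All rates below are therefore assumptions.

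**1. The plan's own safety figure.** Section 9.5.1 claims more than 90% power to halt at a dose when the true rate of grade 3 or higher toxicity is 33%, with 6 people. Under the rule that any one event halts accrual, 1 − 0.67^6 = 0.910, so it reproduces. It is a within-dose rule and compares no doses.

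**2. Width of the planned intervals.** For x events in n, the limits are the 2.5% quantile of Beta(x, n−x+1) and the 97.5% quantile of Beta(x+1, n−x).

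| Events of 12 | 95% interval |
|---|---|
| 0 | 0-26.5% |
| 1 | 0.2-38.5% |
| 2 | 2.1-48.4% |
| 3 | 5.5-57.2% |
| 4 | 9.9-65.1% |

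Check for zero events: 1 − 0.025^(1/12) = 26.5%. A clean dose leaves about one in four not excluded. This width comes mainly from n = 12.

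**3. What the overall rate estimates.** At true rates 2/5/12/30% the average is (2+5+12+30)/4 = 12.25%, about 6 times the 50 mg rate and 0.4 of the 400 mg rate. With counts 0, 0, 1, 4 it is 5/48 = 10.4% (3.5-22.7%); the upper limit lies below the 33% observed at 400 mg.

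**4. Regimen mix over all follow-up.** Participants on the combination schedule after day 14: 50 mg 12/12; 100 mg 4/12; 200 mg 0/12; 400 mg 0/12; overall 16/48 = 33%. On days 1-14 it is 0 at every dose.

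**5. Exact trend test.** Let T be the sum of dose score times events. Given the total S, the p-value is the sum, over tables with T at least as large as observed, of the product of C(12, x_d) divided by C(48, S).

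Example 0, 0, 1, 4: S = 5 and C(48,5) = 1,712,304. The tables as extreme are (0,0,1,4), with 12 × 495 = 5,940, and (0,0,0,5), with 792. p = 6,732/1,712,304 = 0.004, the same with scores 0-3 or 1, 2, 4, 8. The separate intervals at 50 mg (0-26.5%) and 400 mg (9.9-65.1%) overlap.

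Example 0, 0, 0, 2: p = C(12,2)/C(48,2) = 66/1,128 = 0.059.

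Power and error at one-sided 2.5%, from enumerating all 13^4 outcomes. Ranges cover the two score sets:

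| Assumed rates at 50/100/200/400 mg | Rejection probability |
|---|---|
| 2/5/12/30% | 53-56% |
| 20/30/40/60% | 50-54% |
| 2/4/8/15% | about 16% |
| 1/2/5/10% | about 8% |
| flat, 10% to 40% | 1.3-2.2% |

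**6. A tempting alternative.** One could bound the risk at each dose by pooling it with all higher doses, assuming risk never falls with dose. With no events this looks good (0/36 at 100 mg: upper limit 9.7%). With 0, 0, 1, 4 it is worse than the single dose: 29.5% (5/36) against 26.5% at 100 mg, and 42.2% (5/24) against 38.5% at 200 mg.

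**The case against.** The per-dose exact intervals do answer the stated objective. Showing a rising trend is not an objective, since Section 12.1 takes dose-relatedness as background. Dose order is already used in the sequential escalation. The overall rate stands beside the per-dose rates, so a high rate at 400 mg stays visible. These points stand, and they make this an optional improvement.

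A reader might infer that the plan never relates AEs to exposure. It does not go that far: the MARS text links concentrations to AEs, and Section 1 promises that exposure-safety data will be considered. But the MARS text is optional, its note concerns earlier participants at 50 and 100 mg, and it addresses AEs in general rather than related grade 3-4 events and SAEs. Section 1 names no method. Neither fills the gap at 200 and 400 mg.

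A reader might also infer that using dose order would give a much sharper answer on the primary safety endpoint. That is not supported. If events are as rare as the protocol expects, power is around 8-16%, and the pooled upper limit can be wider than the single-dose limit when risk rises.

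Finally, any AE and AEs of grade 2 or higher include the few grade 3-4 events that can stop escalation, so these endpoints are not independent of it. That stands too, and it is why the p-value can only be supportive.

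**Conclusion.** The concern holds in limited form. For a primary objective about different doses, Section 8.1 offers separate intervals and an average, with no comparison across doses. The all-follow-up window mixes dose with regimen for 16 of 48 participants, all at the two lowest doses. The window is the firmer part, since it rests on the documents alone.

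The gain from a trend test is moderate: power of about 50-56% under steep assumed gradients and 8-16% when events are rare, with error below the nominal 2.5% under flat rates. These figures assume 12 evaluable people at every dose; if escalation stops early, fewer doses contribute. They apply to an AE proportion with the assumed rates, and are not a claim about related grade 3-4 events and SAEs. Worth considering.

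**What to change.** In the AE analysis of Section 8.1:

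1. Keep the per-dose Clopper-Pearson intervals, and report AE proportions by dose for events starting on days 1-14 (imatinib alone at all four doses). Report later time by regimen.
2. Add a supportive one-sided exact Cochran-Armitage trend test in dose on the days 1-14 data, for any AE and for AEs of grade 2 or higher. Fix the dose scores in advance. State that both endpoints include grade 3-4 events that can stop escalation, so the p-values are supportive.
3. Show related grade 3-4 events and SAEs by dose, descriptively, and say that the overall rate is not the safety rate of any dose.
4. Do not add upper limits that pool a dose with all higher doses.
5. For the any-AE test, apply one hemoglobin grading rule to all 48 participants: Section 9.2 of Version 5.0 leaves out a grade 1 category, while Section 9.2 of Version 3.0 states no such exception.

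The cost is a few lines of text and a short program, with no new data and no change to dosing or escalation. The downside is an extra supportive analysis on two endpoints, with low power if events are rare.

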12.2 Benefits

There are no direct benefits to the participants. Participants may however feel they experience the indirect benefit of participating in a research study aiming to identify a new treatment for TB.

12.3 Risk Benefit Assessment

Given the public health problem of TB, and the known safety profile of imatinib and the anti-TB drugs under study, we feel that the study has a favorable risk benefit ratio to society.

12.4 Informed Consent Process / HIPAA Authorization

The Principal Investigator or an authorized clinical Co-Investigator will obtain written informed consent in English from all potential participants. The consenting process will take place in a private space in the clinics where participants are recruited, to ensure confidentiality.

Participants will be allowed to provide consent at the time of the consent discussion.

Participants will be given time during the consent discussion to ask and have answered any questions. Informed consent will be documented in accordance with GCP standards.

13 Study Finances

13.1 Funding Source

This study is funded by a UH3 grant awarded to [name] at Emory University, by the National Institutes of Allergy and Infectious Diseases / Division of AIDS.

13.2 Conflict of Interest

Emory investigators will follow the Emory University Policy on Conflicts of Interest Related to Research. All University of Pennsylvania Investigators will follow the University of Pennsylvania Policy on Conflicts of Interest Related to Research.

17.1 Source Documents

Source data is all information, original records of clinical findings, observations, or other activities in a clinical trial necessary for the reconstruction and evaluation of the trial. Source data are contained in source documents. Examples of these original documents, and data records include: hospital records, clinical and office charts, laboratory notes, memoranda, participants' diaries or evaluation checklists, pharmacy dispensing records, recorded data from automated instruments, copies or transcriptions certified after verification as being accurate and complete, microfiches, photographic negatives, microfilm or magnetic media, x-rays, participant files, and records kept at the pharmacy, at the laboratories, and at medico-technical departments involved in the clinical trial.

